Prior to 2017, we performed all cystoscopic Onabotulinum Toxin A injections in the operating room at Mayo Clinic in Rochester, Minnesota. Patients with refractory overactive bladder require repeat injections and had to return to the operating room on average every 6-7 months. This would be almost a whole day's ordeal for patients. In order to minimize the inconvenience to patients and to provide cost effective patient care, Cystoscopic Onabotulinum A injections were transitioned to the office setting in 2017.

For successful adoption of office cystoscopic Onabotulinum Toxin A injection, the procedure has to be an acceptable option to patients. As noted earlier, office cystoscopy in itself is an uncomfortable procedure and the addition bladder injections make it painful. The pain patients experience during the procedure can deter them from wanting a repeat cystoscopic injection in office setting. Currently we use local anesthesia (intra-urethral lidocaine), intra-vesicular lidocaine solution, distraction techniques (conversation/music/’squeeze balls’), and aromatherapy for pain control during this procedure. Despite this, a preliminary review of 91 office Cystoscopic Onabotulinum A injections performed at our institution from 2017 to 2019 showed that the average intra-procedural pain score was 5 on a numerical pain scale of 0 to 10.

Therefore, we chose the pain experienced during the office Cystoscopic Onabotulinum Toxin A injection and the patient’s satisfaction from the procedure as the specific aims for this study.

2 Study Objective(s)/Aims(s):

2.1 *Specific Aim #1: To assess whether the TENS units are effective for intraoperative pain management during office cystoscopic Intradetrusor Onabotulinumtoxin A in women with OAB.*

We plan to compare participant reported pain using a 0-10 numerical pain scale at baseline, during and after cystoscopic intradetrusor onabotulinumtoxin A injection in patients randomized to active TENS units and placebo TENS units. We will compare the change in numerical pain scale from baseline to intraoperatively and intraoperatively to postoperatively between both groups.

[figure not shown]
2.2 *Specific Aim #2: To evaluate the effect of TENS units on participant satisfaction following cystoscopic intradetrusor onabotulinumtoxin A injection in women with OAB.*

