3.5 Primary endpoints

- Numeric Analog Pain Score (0-10) at Baseline before Office Cystoscopic Onabotulinum Toxin A injection (collected after the participant changes into procedural gown)
- Numeric Analog Pain Score (0-10) during Office Cystoscopic Onabotulinum Toxin A injection (collected during middle of the procedure, after the 10th injection)
- Numeric Analog Pain Score (0-10) after Office Cystoscopic Onabotulinum Toxin A injection (collected 5-10 minutes after the procedure)

Source: The Numerical Analog Pain Score will be documented by the study coordinator into the case report forms and later transferred in the Red Caps Data Management system.

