4.4 Withdrawal of Subjects and Follow up

A participant can chose to withdraw from the study at any point. A verbal request is all that is needed and can be conveyed to anyone of the team members taking care of the participant. This information will then be relayed to the study coordinator by the person receiving the request. No further follow up is needed.

5 Study Procedures

A flow chart of study activities is provided in Protocol Section 3.4

5.1 *Visit 1:*

Participants will be recruited from the Division of Urogynecology at Mayo Clinic, where care is being provided. Care providers will determine whether women are interested in learning about the study. The study coordinator will then be notified of women with Overactive Bladder interested in office based Cystoscopic Intra-detrusor Onabotulinum Toxin A injections by the care provider/Registered Nurse during the office visit following their appointment. The study coordinator will then approach the women interested in the study immediately following this appointment. A written informed consent will be obtained from all eligible women who chose to participate using a standardized consent form approved by the Mayo Clinic Institutional Review Board. We will allow for 1 year from the start of recruitment for accrual of participants.

5.2 *Outpatient Procedure Visit: Cystoscopic Onabotulinum Toxin A Injection*

On the day of the scheduled procedural visit, all participants will receive a Generalized Anxiety Disorder 7 (GAD -7) and Depression screening questionnaire (PHQ-9). Those women screening positive for anxiety (GAD 7 score ≥ 10) or depression (PHQ-9 score ≥ 10), will be offered referral to their primary care provider for further management. These women can continue to remain in the study and will not be excluded. In the same questionnaire, the participants will be asked “Have you ever experienced sexual abuse?” in order to assess for a history of sexual abuse. Participants will also be asked “Have you experienced chronic, unrelenting pain for 6 months or more duration?” in order to assess for a history of chronic pain.

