Participants will be randomized to two groups using a computerized sequence generator based on permuted block randomization (1:1 allocation ratio) on the day of the procedure by the registered nurse (RN) taking care of the participant. Participants in Group 1 will receive an Activated TENS unit for pain control. Participants in Group 2 will have a Sham, inactive TENS unit for pain control. Both groups will be blinded to the type of TENS unit received. The nursing team taking care of the participant will know about the randomization. The care providers performing the procedure and the study coordinator will not be notified about the randomization.

On the day of the procedure, after baseline questionnaires and randomization, the participant will receive intraurethral lidocaine jelly as part of the standard pain control measures. Her bladder is then emptied using a Foley Catheter, and at the same time the bladder is then backfilled with 30 ml (300 mg/30 ml) of 1 % plain lidocaine solution. A waiting period of 30-50 minutes duration is allowed for the intravesicle lidocaine to take effect. During this wait period, participant is asked to lie supine for 10-15 minutes, then roll to the left side for 10-15 minutes and then to right side for about 10-15 minutes.

The participant, the provider taking care of the participant and the study coordinator assigned to the study will be blinded to the randomization. Both groups of participants will receive the TENS unit electrode placement during this wait period by the RN.

In participants randomized to the Active TENS group, the TENS unit will be initiated on standard setting (see ‘TENS, Electrode Placement, and Settings’) 5 minutes before starting the cystoscopy and will last the duration of the cystoscopy. The device intensity (amplitude) will be individually adjusted to each participant’s maximum sensory level, which is the strongest reported tingling feeling without pain and muscle contractions and kept at this setting for the duration of the procedure.

Participants randomized to the Sham TENS group will not receive the TENS therapy. Instead, they will receive electrode placement followed by initiation of the TENS unit until the participant feels the tingling sensation, following which the TENS unit will be immediately turned off by the RN. The participant will be notified by the RN that the TENS stimulus has been turned down such that they are not able to feel the tingling sensation anymore.

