5.3 Masking/Blinding

Participants in both arms of the study will be blinded to whether they received Active TENS unit or Sham TENS unit. Only the nursing team will be notified about the randomization. The care providers performing the procedure and the study coordinator will not be notified about the randomization. The study coordinator will ask the participant and the provider separately (in the absence of the other) whether they felt the participant was in the Active TENS group versus the Sham TENS group at the end of the procedure.

Schedule of Events		
Study Activity	Visit 1 Outpatient Clinic	Visit 2 Outpatient Procedure Cystoscopic Onabotulinum Toxin A Injection
Screening and Informed Consent	X	
Depression and Anxiety Screen		X
Randomization		X
Numerical Pain Score assessment		X
Participant Satisfaction Assessment		X
Participant and Provider Perception regarding Arm of study		X

6 Statistical Plan

6.1 *Sample Size Determination:*

Based on our baseline preliminary data and the study ‘Transcutaneous Nerve Stimulation for Pain Relief During Office Hysteroscopy’ by Lison et al (2017)[6], power calculations were performed. As estimates of the mean and variance of the pain scale we used table 2 from the Lison et al (2017) study and our preliminary data. Group sample sizes of 27 and 27 achieve 80.53% power to reject the null hypothesis of equal means when the population mean difference is $\mu_1 - \mu_2 = 4.0 - 2.0 = 2.0$ with standard deviations of 2.0 for group 1 and 3 for group 2, and with a significance level (alpha) of 0.050 using a two-sided two-sample unequal-variance t-test. With a 10% possible dropout rate, we plan to have 30 participants in each of the study.

6.2 *Statistical Methods:*

6.2.1 **Specific Aim #1: To assess whether the TENS units is effective for intraoperative pain management during office cystoscopic Intradetrusor Onabotulinumtoxin A in women with OAB.**

We plan to compare participant reported pain using a 0-10 numerical pain scale at baseline, during and after cystoscopic intradetrusor onabotulinumtoxin A injection in participants randomized to active TENS units and placebo TENS units. We will compare the change in numerical pain scale from baseline to intraoperatively and intraoperatively to postoperatively between both groups.

Hypothesis: We hypothesize that there will be a clinically significant pain reduction in the Active TENS group.

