Interpretation: Assuming that pain as measured is decreased in the Active TENS group when compared to the placebo TENS group, then we will accept our hypothesis. If not, we will perform a subgroup analysis of our data to see if certain groups of people that have better pain reduction with the Active TENS unit and an analysis of risk factors that might contribute to pain with Intradetrusor Onabotulinumtoxin A injection.

Power Calculation: Based on our baseline preliminary data and the study ‘Transcutaneous Nerve Stimulation for Pain Relief During Office Hysteroscopy’ by Lison et al (2017)(6), power calculations were performed. As estimates of the mean and variance of the pain scale we used table 2 from the Lison et al (2017) study and our preliminary data. Group sample sizes of 27 and 27 achieve 80.53% power to reject the null hypothesis of equal means when the population mean difference is $\mu_1 - \mu_2 = 4.0 - 2.0 = 2.0$ with standard deviations of 2.0 for group 1 and 3 for group 2, and with a significance level (alpha) of 0.050 using a two-sided two-sample unequal-variance t-test.

Data Analysis: The data will be analyzed using an intention-to-treat approach. In order to account for individual participant pain sensitivity profiles through the experiment, random effect longitudinal model will be adjusted to the data controlling by treatment and selected covariates at baseline.

6.2.2 Specific Aim # 2: To evaluate the effect of TENS units on participant satisfaction following cystoscopic intradetrusor onabotulinumtoxin A injection in women with OAB.

We plan to evaluate participant satisfaction on a 10 point Likert scale immediately after the procedure in participants randomized to activated TENS units and placebo TENS units.

Hypothesis: There will be a high level of participant satisfaction on a 10 point Likert scale in the active TENS group.

Interpretation: Assuming that the participant satisfaction as measured is high in the Active TENS group, then we will accept our hypothesis. If not, we plan to do a subgroup analysis to see if there are factors that contribute to higher participant satisfaction in certain groups of people in both the Active TENS and Placebo TENS group.

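### Aim 1 compares change from baseline without committing to adjustment for baseline pain, so its precision depends on a baseline SD and correlation that the plan does not give

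*Combined protocol and SAP*

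**What the plan says.** Section 6.2.1 (and 2.1) sets out the Aim 1 comparison: "We will compare the change in numerical pain scale from baseline to intraoperatively and intraoperatively to postoperatively between both groups". Under Data Analysis, 6.2.1 names one model: a "random effect longitudinal model will be adjusted to the data controlling by treatment and selected covariates at baseline". The covariates are not listed. Section 3.5 lists the baseline pain score as one of three primary endpoints, "collected after the participant changes into procedural gown", so an analyst could treat it as an outcome or as a covariate.

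The only power figure, in 6.1 and again in 6.2.1, is 80.53% with 27 per arm for means of 4.0 and 2.0 and SDs of 2 and 3, "using a two-sided two-sample unequal-variance t-test". On the source of these values the plan says: "As estimates of the mean and variance of the pain scale we used table 2" of a cited hysteroscopy trial, together with preliminary data. No time point, baseline SD or correlation is given. Section 1.6 summarises the preliminary data by saying that "the average intra-procedural pain score was 5 on a numerical pain scale of 0 to 10".

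**The concern.** The test that was powered and the comparison that is described are not shown to be the same. A change score carries the variance of the baseline score as well as that of the intraoperative score, less twice their covariance. If baseline pain varies appreciably and is only weakly related to injection pain, subtracting it adds noise.

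The baseline score is taken at gowning, before any instrumentation, so a weak correlation cannot be ruled out. Nor can a negligible spread be assumed: the exclusion criteria in 4.2 do not mention chronic pain, and 5.2 has participants asked "Have you experienced chronic, unrelenting pain for 6 months or more duration". In a 60-participant trial planned at about 80% power, a loss of precision would matter. It can be avoided with a score the trial already collects.

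**Working it through.** **Inputs from the documents (6.1):** difference d = 2.0; SDs 2 and 3; n = 27 per arm evaluable, 30 planned; two-sided alpha 0.05; unequal-variance t-test.

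**Assumptions, not in the documents:** the means and SDs are raw intraoperative scores; baseline SD b is the same in both arms, as randomisation implies in expectation; rho is the same in both arms.

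**1. The plan's own figure.** SE = sqrt((4 + 9)/27) = 0.694. Noncentrality = 2.0/0.694 = 2.882, with Satterthwaite df 45.3. Noncentral t power is 80.53%, as stated. With 30 per arm it is 84.6%.

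**2. Change score.** In an arm with intraoperative SD s, Var(change) = s² + b² − 2·rho·s·b. Summed over both arms, the variance moves from 13 to 13 + 2b² − 2·rho·b·(2 + 3).
- b = 2, rho = 0.2: arm variances 6.4 and 10.6, sum 17.0; SE = sqrt(17/27) = 0.793; noncentrality 2.521; power 69.5%.
- b = 1, rho = 0.4: arm variances 3.4 and 7.6, sum 11.0; SE = sqrt(11/27) = 0.638; noncentrality 3.133; power 86.6%.

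Setting 2b² = 10·rho·b gives a break-even at rho = b/5. The numerical roots are almost the same (0.199 for b = 1, 0.398 for b = 2).

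**3. Change-score power (%) with 27 per arm.**

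| b | rho 0 | rho 0.2 | rho 0.4 | rho 0.6 |
|---|---|---|---|---|
| 0.5 | 79.1 | 82.0 | 85.0 | 88.0 |
| 1 | 74.8 | 80.6 | 86.6 | 92.3 |
| 1.5 | 68.2 | 76.2 | 85.1 | 93.7 |
| 2 | 60.4 | 69.5 | 80.6 | 92.4 |
| 2.5 | 52.3 | 61.5 | 73.5 | 88.2 |

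At rho 0.2 to 0.6, 4 of the 15 cells are below 80.53% and 11 are above. At rho 0 all five are below.

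**4. Baseline-adjusted regression.** The intraoperative score is regressed on arm and baseline score, with HC2 standard errors and 51 df. In simulation (normal scores, b = 1 and 2) power is about 80% at rho 0, 81% at 0.2, 86% at 0.4 and 93% at 0.6. These values do not depend on b, because rescaling the covariate leaves the fit unchanged. Null rejection is about 5%. At rho 0, adjusted power is 79.7 to 80.0% depending on the df used, which is 0.6 to 0.8 point below 80.53%.

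**5. The longitudinal model.** Suppose baseline is modelled as an outcome with free means in each arm and the data are complete. The arm-by-time contrast is then the difference in mean changes, so the model does not by itself recover the gain. Constraining baseline means equal can recover it, but a plain random-intercept model forces one variance and one correlation across times and arms. In simulations of that model with constrained baseline means, a true null was rejected in about 9 to 16% of trials in one set and 12 to 17% in a second, small set (200 trials per cell). The first set assumed b = 1 or 2, postoperative SD 0.7 times intraoperative, intraoperative-to-postoperative correlation 0.5 and baseline correlations 0 to 0.6. These rates show the direction of the problem and are not a forecast for this trial.

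**The case against.** The strongest objection is that the power gap is conditional. If 4.0 and 2.0 with SDs 2 and 3 already describe changes, 80.53% is the power of the change test and step 3 does not apply. The wording in 6.1 and the preliminary average in 1.6 lean towards raw scores but do not decide it. This stands, and it is why the result is stated as conditional.

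Second, the documents attach the t-test only to the sample size calculation. The named analysis is the longitudinal model, and its selected covariates may include baseline pain. That is possible, but the plan does not commit to it, and step 5 shows that the model alone does not supply the adjustment.

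Third, most cells at rho 0.2 to 0.6 favour the change score over the unadjusted score, and the largest losses need a wide baseline spread with weak correlation. This also stands. A reader might infer that the trial is underpowered, or that comparing changes is biased or always weaker. The documents support none of these: the contrast is unbiased under randomisation, above the break-even it gains power, and b and rho are unknown.

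Finally, adjustment is safe only if the baseline score precedes treatment. The timing in 3.5 indicates that it does, and 5.2 starts active TENS "5 minutes before starting the cystoscopy and will last the duration of the cystoscopy". However, 3.5 has the study coordinator document the pain scores, while 5.2 has the coordinator enter the room after TENS initiation. This needs confirming.

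**Conclusion.** The point holds as a matter of efficiency and specification. The plan describes a change-from-baseline comparison, leaves its covariates open, and gives one power figure without saying what its means measure. If they are raw intraoperative scores, with a common baseline SD and common correlation, change-score power at 27 per arm may fall on either side of 80.53%, with the turning point near rho = b/5. Adjusted regression removes that dependence on b. It is at worst about one point below the stated figure, and it exceeds it from a correlation between 0.1 and 0.2 upward. If the values are changes, 80.53% applies to the change test directly. Adjustment is then still no less efficient, apart from about one degree of freedom. The 80.53% is arithmetically correct for the test it names.

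**What to change.** **In 6.2.1,** replace the baseline-to-intraoperative change comparison with this: the between-arm difference in the intraoperative pain score (after the 10th injection), adjusted for baseline pain score by linear regression with HC2 standard errors, two-sided alpha 0.05, by intention to treat.

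If the longitudinal model is kept for this contrast, enter baseline pain as a covariate or constrain baseline means equal across arms. Either way, specify an unstructured covariance that differs by arm, or a small-sample robust variance. A plain random-intercept model is not an equivalent choice.

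Keep the intraoperative-to-postoperative comparison as planned. Whether it is primary or secondary is for the sponsor to decide, and 3.5 should agree with that decision.

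**In 6.1,** state whether 4.0 and 2.0 are raw scores or changes, and at what time point. If raw, label 80.53% as the unadjusted single-score figure.

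**In 3.5 and 5.2,** confirm that the baseline score is recorded before the TENS unit is started in either arm.

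**Cost:** no new data or participants; about one degree of freedom, or roughly 0.6 to 0.8 point of power at zero correlation. HC3 would be more conservative, with null rejection of about 4.5% and about 1 to 2 points less power.

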3.6 Secondary Endpoints

- Participant satisfaction on a Likert Scale of 1 - 10 (10 = Completely satisfied and 1 = Completely Dissatisfied) after the Office Cystoscopic Onabotulinum Toxin A injection (collected 5-10 minutes after the procedure)
- Depression Screen Score (PHQ 9)
- Anxiety Screen Score (GAD 7)
- History of Sexual Abuse
- History of Chronic Pelvic Pain
- Participant Demographics: Age, Ethnicity, Basal Metabolic Index (BMI), Insurance
- Co-morbid conditions
- Current Medications
- Smoking Status
- Past or Current Illicit Drug Abuse
- Presence of Chronic Pain
- Number of Previous Onabotulinum Toxin A injection
- Previous Therapies for OAB (Lifestyle, Medication, Peripheral Tibial Nerve Stimulation, Sacral neuromodulation)

Source: The Participant Satisfaction Score, PHQ 9 score and GAD 7 score will be documented by the study coordinator into the case report forms and later transferred in the REDCap Data Management system. The participant demographics, co-morbid condition, current medications, smoking status, history of past or current illicit drug abuse, presence of chronic pain, number of previous Onabotulinum Toxin A injections, and previous therapies for OAB will be extracted from the electronic medical records. This information will be transferred to the REDCap Data Management System by the Principal and Co-investigators on the study.

4 Subject Selection Enrollment and Withdrawal

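### Subgroups are examined only if Aim 1 is not met, and then in search of TENS benefit, with no fixed factor list, interaction test or exploratory label

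*Combined protocol and SAP*

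**What the plan says.** Section 6.2.1 (Interpretation) gives the decision rule for Aim 1: "Assuming that pain as measured is decreased in the Active TENS group when compared to the placebo TENS group, then we will accept our hypothesis". The next sentence covers the other outcome: "If not, we will perform a subgroup analysis of our data to see if certain groups of people that have better pain reduction". It continues by naming the target of the search and a companion analysis: "better pain reduction with the Active TENS unit and an analysis of risk factors that might contribute to pain". No subgroup analysis is planned for the case in which the hypothesis is accepted.

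Section 6.2.2 (Interpretation) has a parallel clause for satisfaction: "If not, we plan to do a subgroup analysis to see if there are factors that contribute to higher participant satisfaction". It covers both the active and the placebo arm, so it is not aimed at TENS benefit.

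Neither section names a subgroup factor, a cut-point, a number of tests, an interaction test or a subgroup significance level, and neither calls the analysis exploratory. The Aim 1 model adjusts for baseline covariates that are not named, so the model does not define the subgroups either. Section 3.6 lists, under secondary endpoints, 12 lines of baseline characteristics, such as the PHQ-9 and GAD-7 scores, chronic pain and "Number of Previous Onabotulinum Toxin A injection". Splitting the demographics line into its four items makes 15. The plan does not label them as subgroups, but the data will be available.

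**The concern.** An analysis that is run only after a disappointing result, and is designed to find where the treatment worked, gives a one-sided picture. After a null result the reader sees the groups that look favourable. After a positive result nobody is asked to check whether the effect is consistent. With no list and no interaction test, the number of cuts is open and a difference inside one subgroup can be mistaken for evidence of effect modification.

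The situation is a realistic one. Section 1.4 describes an earlier randomised trial of TENS at flexible cystoscopy that found no difference, although the protocol attributes this to suboptimal settings. Section 1.5 expects the results to be extrapolated to other office procedures, so a chance subgroup could carry weight.

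**Working it through.** **Inputs from the plan (sections 6.1 and 6.2.1).** "Group sample sizes of 27 and 27 achieve 80.53% power to reject the null hypothesis of equal means"; difference 2.0 points; "with standard deviations of 2.0 for group 1 and 3 for group 2"; "with a significance level (alpha) of 0.050 using a two-sided two-sample unequal-variance t-test"; 30 per arm after allowing for 10% dropout. The documents state no subgroup error rate.

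**Inputs that must be assumed.** The number of factors (3 to 15 binary factors, 15 being the section 3.6 count); how each is tested (Welch test in each level at two-sided 0.05); and what counts as failing Aim 1.

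**Step 1: the plan's own figure.** SE = sqrt((2² + 3²)/27) = 0.694 and 2.0/0.694 = 2.88. With Satterthwaite df of 45.3, the noncentral t gives 80.53%, as stated. Enrolment is 27/0.9 = 30 per arm. The sample size is not in dispute.

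**Step 2: chance of a false pro-TENS subgroup.** Treating tests as independent overstates the rate. Ten binary factors give 20 tests, and 1 - 0.975^20 = 39.7%, but all the subgroups are cut from the same women, so the tests are correlated. The rates were therefore simulated: no treatment effect, independent binary factors, one outcome, and a hit if any level favours TENS at two-sided p < 0.05. The first and last data columns are conditional on no significant overall benefit. The middle column is conditional on a point estimate that is not lower on TENS.

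| Factors | Trigger: main test not significant | Trigger: point estimate not lower on TENS | Non-significant trigger, interaction p < 0.05 also required |
|---|---|---|---|
| 3 | 8-10% | 1% | not computed |
| 4 | 11% | 1% | 6% |
| 5 | 13% | 1% | 8% |
| 8 | 18% | 2% | 11% |
| 10 | 20% | 2-3% | 13% |
| 15 | 25% | 3-4% | 18% |

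Using 27 rather than 30 per arm, SDs of 2 and 3, or 30% prevalence moves the first data column by about 1 point or less. A latent correlation of 0.4 between factors lowers it by 1 to 2 points (23% at 15 factors). As a yardstick, a two-sided 0.05 main test favours TENS by chance in 2.5% of null trials.

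**Step 3: ability to find real effect modification.** For two equal subgroups (27/2 = 13.5 per arm in each), the SE of the difference between the two treatment effects is sqrt(2 × 13/13.5) = 1.39. Power for a true 2-point interaction is about Φ(2/1.39 - 1.96) = Φ(-0.52) = 30%. For 80% power the interaction would have to be about (1.96 + 0.84) × 1.39 = 3.9 points on a 0-10 scale. Within a single half-size subgroup of 15 per arm, power for the planned 2-point effect is about 54%.

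**Step 4: what interaction testing alone would do.** With 3 factors and no true effect, at least one interaction reaches p < 0.05 in either direction in about 1 - 0.95³ = 14% of trials; with 10 factors the simulated figure is 40%. An interaction test is therefore not enough without a short list and an exploratory label.

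**The case against.** The strongest objection is to the numbers. The decision sentence in section 6.2.1 asks only whether pain is decreased and mentions no significance test. Taken literally, a null trial that leans towards TENS is accepted and never reaches the subgroup search, so the rate is about 1-4%. This stands as a limit on any headline figure. It does not rescue the plan: the rate is low only because, with no true effect, about half of trials lean towards TENS and would already have been accepted. The significance reading is also plausible, since the sample size rests on a two-sided 0.05 test and the hypothesis speaks of clinically significant reduction. The documents do not settle which is meant.

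The factor count and the within-level Welch tests are likewise assumptions. The plan does not say how subgroups will be tested, its stated Aim 1 analysis is a longitudinal random-effect model, and some section 3.6 items overlap or are not binary.

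Three stronger readings are tempting but not supported:

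- A reader might infer that the plan lets a favourable subgroup rescue the efficacy claim. Section 6.2.1 ties acceptance to the overall comparison, and nothing lets a subgroup restore it. What is missing is an explicit statement to that effect.
- A reader might infer that Aim 2 is a second search for TENS benefit. Its clause looks for factors in both arms, and no pro-TENS error rate was computed for satisfaction.
- A reader might infer that a subgroup look is ruled out after a positive result. It is not planned, but it is not forbidden.

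**Conclusion.** The core point holds: the Aim 1 subgroup analysis depends on the result, looks in one direction and has no specified content. Aim 2 shares the dependence on the result but not the direction.

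The size is conditional. Under a non-significance trigger with within-level testing, the chance of a false pro-TENS subgroup runs from about 8-10% (3 factors) to 25% (15 factors). Under the literal trigger it is about 1-4%. A reader might quote a flat one-in-five risk. That figure corresponds to about 10 factors under the first trigger and cannot be derived from the documents. Nor does 30% interaction power show that most findings would be noise, since that would need an assumption about how common true effect modification is. It does show that the search is poorly placed to detect a real 2-point difference between subgroups.

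The primary comparison, sample size and data collection are unaffected, so this should be fixed but does not undermine the trial.

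**What to change.** Replace the conditional subgroup rules in sections 6.2.1 and 6.2.2 with one rule that applies whatever the main result:

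- Name a short list of baseline factors that are already collected, with any cut-points. The sponsor should choose it before unblinded results are seen, including any by-arm efficacy data shown at the interim review after 30 participants.
- For each factor, report the treatment-by-factor interaction estimate with its 95% confidence interval.
- Label these analyses exploratory, and state that no subgroup result changes the Aim 1 or Aim 2 conclusion.
- Run the analysis of risk factors for pain regardless of outcome, in both arms, with treatment in the model.

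The cost is a few sentences in section 6.2 and a few model terms, with no new data. The downside is that the sponsor gives up an open-ended search after a null result.
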